Clinical Study Protocol

CCP-020 (Diacerein 1%) Topical Ointment

Sponsor Protocol No. CCP-020-102

TKL Study No. DS310717

A 21-Day, Randomized, Controlled Study to Evaluate the Skin Irritation Potential of CCP-020 (Diacerein 1%) Topical Ointment in Healthy Subjects Using a Cumulative Irritant Patch Test Design

Author:

[REDACTED]

Clinical Study Protocol

Development Phase:

1

Document Date:

23-October-2017

Document Status

Amendment 1

Number of Pages:

38

Property of **Castle Creek Pharmaceuticals, LLC.**

Confidential

May not be used, divulged, published, or otherwise disclosed
without the consent of **Castle Creek Pharmaceuticals, LLC.**

Synopsis

Study Title:	A 21-Day, Randomized, Controlled Study to Evaluate the Skin Irritation Potential of CCP-020 (Diacerein 1%) Topical Ointment in Healthy Subjects Using a Cumulative Irritant Patch Test Design
TKL Study Number:	DS310717
Sponsor Protocol Number:	CCP-020-102
Sponsor:	Castle Creek Pharmaceuticals, LLC
Development Phase:	1
Study Objectives:	To evaluate the irritation potential of CCP-020 (Diacerein 1%) topical ointment on normal skin.
Study Design:	Single center, randomized, controlled, evaluator blinded, within-subject comparison study.
Planned Sample Size:	30 evaluable subjects
Study Population	Healthy adult males and females volunteer subjects
Investigational Products:	CCP-020 (Diacerein 1%) topical ointment, approximately 0.2 mL, applied topically under occlusive patch conditions to the infrascapular area of the back, once daily for 21 consecutive days over 3 weeks Vehicle, approximately 0.2 mL, applied topically under occlusive patch conditions to the infrascapular area of the back, once daily for 21 consecutive days over 3 weeks
Concurrent Controls:	A solution of 0.2% sodium lauryl sulfate (SLS), approximately 0.2 mL applied topically under occlusive patch conditions to the infrascapular area of the back, once daily for 21 days over 3 weeks, will serve as a positive control. A solution of 0.9% saline, approximately 0.2 mL applied topically under occlusive patch conditions to the infrascapular area of the back, once daily for 21 consecutive days over 3 weeks, will serve as a negative control.
Efficacy Evaluation Criteria:	Not Applicable
Safety Evaluation Criteria:	All local and systemic adverse events (AEs) observed by or reported to the Investigator throughout the study will be evaluated. The intensity, duration, and causal relationship to the investigational patch are to be rated for all AEs.
Statistical Methods:	Cumulative irritancy will be quantified for each subject/product by the mean and total cumulative irritancy score. This parameter will be tested pair wise for product differences using analysis of variance (subject, product).
Number of Study Centers:	Single center

Signature page

Product names: **CCP-020 (Diacerein 1%) Topical Ointment**
Vehicle

[figure not shown]
TKL Study number: **DS310717**

Sponsor protocol number: **CCP-020-102**

The signatures of the representatives on the following page constitute their approval of this protocol and provide the necessary assurances that this study will be conducted according to all stipulations stated in the protocol, including all statements as to confidentiality. It is also agreed that the study will not be initiated without the approval of an appropriate Institutional Review Board.

Approved by the following:

Sponsor

Signature page for the Principal Investigator

[figure not shown]
Product names: CCP-020 (Diacerein 1%) Topical Ointment

Vehicle

TKL Study number: DS310717

Sponsor protocol number: CCP-020-102

I have read this protocol and agree to conduct this study in accordance with all stipulations of the protocol and in accordance with the Declaration of Helsinki.

Investigators and study administrative structure

This figure consists of a 10x3 grid of horizontal bar charts. Each cell in the grid contains a black bar. The length of the bars varies, indicating data values. The bars are positioned at different heights within each cell, suggesting multiple data series or conditions per cell. The grid is defined by vertical and horizontal lines, creating a structure of 10 rows and 3 columns.

TABLE OF CONTENTS

Signature page.....	3
Signature page for the Principal Investigator.....	4
Investigators and study administrative structure.....	5
List of Abbreviations	9
1. INTRODUCTION	10
1.1. Background Information.....	10
1.2. Rationale for the Study	10
2. STUDY OBJECTIVES	12
3. INVESTIGATIONAL PLAN.....	13
3.1. Study Design.....	13
3.2. Discussion of Design	13
3.3. Study Population.....	13
3.3.1. Subject Population	13
3.3.2. Inclusion and Exclusion Criteria	13
3.3.3. Interruption or Discontinuation of Treatment.....	15

1. INTRODUCTION

This study investigates the irritation potential of CCP-020 (Diacerein 1% topical ointment) under standardized conditions compared with a known irritant (0.2% sodium lauryl sulfate, SLS) and an inert control (normal saline). Because CCP-020 (Diacerein 1%) topical ointment is formulated for topical use, it is necessary to determine the potential of this product to cause irritation after repeated topical application to the skin.

The study will be conducted in compliance with Food and Drug Administration (FDA) regulations, the ethical principles of the Declaration of Helsinki concerning medical research in humans (Recommendations Guiding Physicians in Biomedical Research Involving Human Subjects, Helsinki 1964 and amendments 2013), the International Conference on Harmonization (ICH) – Good Clinical Practice (GCP) Guidelines as currently amended, and all applicable standard operating procedures (SOPs) of TKL Research, Inc. (TKL).

1.1. Background Information

CCP-020 (previously developed as AC-203) is a topical ointment containing diacerein (4,5-bis[acetoxy]-9,10-dihydro-9,10-dioxo-2-anthracene carboxylic acid; also known as diacetyl-rhein), a highly purified anthraquinone derivative, and is being developed by Castle Creek Pharmaceuticals for the treatment of epidermolysis bullosa simplex (EBS). The capsule formulation of diacerein, intended for oral use and systemic absorption, was initially approved for use in osteoarthritis (OA) in France in 1992 (as Artodar[®], ART50[®], or Zondar[®]). Since then, it has received marketing authorization in over 30 countries in Europe, South America, and Asia. It is classified as a Symptomatic Slow-Acting Drug in OA. Following oral administration of the capsule formulation, diacerein is rapidly metabolized to the deacetylated active metabolite, rhein. Similarly, diacerein in the topical formulation is hydrolyzed to rhein in the epidermis and the dermis following administration. Diacerein and rhein have been shown to inhibit the in vitro and in vivo production and activity of interleukin (IL)-1 β and other proinflammatory cytokines. It has a novel mode of action that differentiates it from non-steroidal anti-inflammatory drugs (NSAIDs) and other conventional forms of drug therapy.

For the development of CCP-020, a total of 10 animal studies have been conducted with CCP-020 ointment 1%, including one skin penetration study, three acute dermal toxicity studies, one phototoxicity study, three pharmacokinetic studies, and two sub-chronic juvenile toxicity studies. CCP-020 was well-tolerated in these studies and no untoward adverse effects were noted. To date, two clinical studies of CCP-020 have been completed in patients with epidermolysis bullosa simplex (EBS). These include a Phase one pilot study in five patients and a Phase 2, multiple-site study in 17 patients in Europe. The Phase 2 study demonstrated CCP-020 was well-tolerated and no treatment-related adverse events (AEs) were reported. The Investigator's Brochure should be consulted for summaries of the results of these studies.¹

This Phase 1 study will assess the irritation potential of CCP-020 (Diacerein 1%) topical ointment.

1.2. Rationale for the Study

This is a clinical study in-humans treated with CCP-020 (Diacerein 1%) topical ointment intended to determine the cumulative irritation potential of CCP-020 (Diacerein 1%) topical

ointment treatment on normal human skin in healthy volunteers using a cumulative irritancy patch test (CIPT) design.

Substances that come into contact with human skin need to be evaluated for their propensity to irritate with a reproducible, standardized, quantitative patch evaluation procedure that demonstrates the study material can be applied safely to human skin without significant risk of adverse reactions.²

Cumulative irritancy patch evaluation is a modified primary irritancy test, which can detect irritants that require multiple applications to cause a skin reaction. These reactions are due to direct damage to the epidermal cells and no immunologic (allergic) mechanism is involved. This procedure may detect so-called “fatiguing substances,” which are mild irritants that cause more strongly positive reactions with successive multiple skin exposure.

2. STUDY OBJECTIVES

The primary objective of this study will be to determine the potential of CCP-020 (Diacerein 1%) topical ointment to cause skin irritation after repeated topical application to the healthy skin of humans under controlled conditions.

In addition, safety will be assessed by evaluation of any AEs reported during the study.

3. INVESTIGATIONAL PLAN

3.1. Study Design

This will be a randomized, single-center, controlled, evaluator-blinded, within-subject comparison study of the investigational products (IPs) (CCP-020 [Diacerein 1%] topical ointment and vehicle), and positive and negative controls under occlusive conditions in healthy volunteer subjects. All subjects will have fields designated for the IP patches and the positive and negative control patches at 4 randomly assigned, adjacent sites, for the purpose of determining irritation potential.

The IPs and controls will be applied to one side of the infrascapular area of the back. Evaluation of dermal reactions at the application sites will be assessed clinically using a visual scale that rates the degree of erythema, edema, and other signs of cutaneous irritation (see [Section 3.5.5](#)).

A total of 21 consecutive applications of each product will be made over a study period of 22 days.

3.2. Discussion of Design

This study design is based on the Modified Berger procedure, and is an accepted standard methodology used for assessment of cumulative irritation potential.³

The IPs in the study will be CCP-020 (Diacerein 1%) topical ointment and vehicle. The positive and negative controls will be 0.2 mL of 0.2% SLS and 0.2 mL of 0.9% saline, respectively, applied topically under occlusive conditions.

3.3. Study Population

3.3.1. Subject Population

A sufficient number of subjects will be enrolled in order to provide 30 completed subjects evaluable for analysis; an individual subject will be allowed to participate in the study one time only.

A rationale for the choice of sample size is provided in [Section 4.2](#) of this protocol.

3.3.2. Inclusion and Exclusion Criteria

Inclusion Criteria

A subject will be considered eligible for participation in the study if all of the following inclusion criteria are satisfied prior to randomization:

1. Is a healthy male or female (to be confirmed by medical history);
2. Is 18 years of age or older;
3. In the case of a female of childbearing potential, is using two acceptable forms of birth control (oral/implant/injectable/transdermal contraceptives, intrauterine device, condom with spermicide, diaphragm with spermicide, abstinence, partner's vasectomy, tubal ligation). Abstinence or vasectomies are acceptable if the female subject agrees to

implement two of the other acceptable methods of birth control if her lifestyle/partner changes;

4. In the case of a female of childbearing potential, has a negative urine pregnancy test (UPT) on Day 1 prior to randomization and are willing to submit to a UPT at the end of study (EOS);
5. Is free of any systemic or dermatological disorder, which, in the opinion of the Investigator, will interfere with the study results or increase the risk of AEs;
6. Is of any Fitzpatrick Skin Type or race, providing the skin pigmentation will allow discernment of erythema (see [Table 1](#));
7. Complete a medical screening procedure; and
8. Read, understand, and sign an informed consent.

Exclusion criteria

A subject who has any of the following will be excluded from the study:

1. Has any visible skin disease at the application site which, in the opinion of the Investigator, will interfere with the evaluation of the test site reaction;
2. Is using systemic/topical corticosteroids within 3 weeks prior to and/or during the study, or systemic/topical antihistamines 72 hours prior to and during the study;
3. Is not willing to refrain from using systemic/topical anti-inflammatory analgesics such as aspirin (81 mg daily aspirin will be allowed), Aleve, Motrin, Advil, or Nuprin for 72 hours prior to and during the study (occasional use of acetaminophen will be permitted);
4. Is using medication which, in the opinion of the Investigator, will interfere with the study results (e.g. anti-inflammatory medications, antipsychotics, anticonvulsants with potential pain relief effects, immunomodulatory medications, and others);
5. Is unwilling or unable to refrain from the use of sunscreens, cosmetics, creams, ointments, lotions or similar products on the back during the study;
6. Has psoriasis and/or active atopic dermatitis/eczema;
7. Has a known sensitivity or allergy to constituents of the materials being evaluated including diacetoin, mineral oil, petrolatum, cetyl alcohol, D&C Yellow #10 and/or ethyl paraben;
8. Is a female who is pregnant, plan to become pregnant during the study, or is breast feeding a child;
9. Has damaged skin in or around the test sites, including sunburn, excessively deep tans, uneven skin tones, tattoos, scars, excessive hair, numerous freckles, or other disfigurements of the test site;
10. Has received treatment for any type of internal cancer within 5 years prior to study entry;
11. Has a history of, or are currently being treated for skin cancer and/or hepatitis;
12. Has a history of, or is currently being treated for, insulin dependent diabetes;

13. Has any condition that might compromise study results;
14. Currently or expect to sunbathe or use tanning salons during the study;
15. Is currently participating in any clinical testing;
16. Has any known sensitivity to adhesives; and/or
17. Has received any investigational drug(s) within 4 weeks prior to study entry.

3.3.3. Interruption or Discontinuation of Treatment

In accordance with legal requirements and ICH-GCP guidelines, every subject or his/her legal representative has the right to refuse further participation in the study at any time and without providing reasons (see also [Section 5.3](#)). A subject's participation is to be terminated immediately upon his/her request. The Investigator should seek to obtain the reason and record this on the case report form (CRF).

If at the time of refusal a study product has already been administered, the subject should be advised on follow-up safety investigations. If a subject withdraws from the study, all efforts will be made to complete a final evaluation if possible. Subjects discontinued for having experienced an AE will be followed until the AE is resolved, a reasonable explanation is provided for the event, or the subject is referred to his/her own primary medical doctor (PMD). The specific AE in question will be recorded on the appropriate CRF.

If a subject develops a serious adverse event (SAE), his/her termination from the study will be considered by the Investigator. Similarly, if the subject develops conditions over the course of the study which would have excluded his/her entry in the study according to the safety-related medical exclusion criteria, he/she must be withdrawn immediately.

The subject may be withdrawn from the study at any time at the discretion of the Investigator for medical reasons and/or due to non-adherence to the treatment scheme and other duties stipulated in the study protocol. The reasons are to be documented on the CRF.

Individual patches may be discontinued if a reaction of a grade of 3 or greater (see [Section 3.5.5](#) for examples of values using additive grades from [Tables 3](#) and [Table 4](#)) occurs at any point during the study. Further patch applications of that product on that individual subject will be terminated. A “not patched” (NP) symbol and a score of 3 will be assigned for all subsequent days.

If a reaction is observed in any induction evaluation, a change in site location for the remaining applications in the Induction Phase will take place for that particular patch. See [Section 3.5.5](#) for interpretations of scores.

In addition, the Sponsor retains the right to end the study at any time if the study cannot be carried out as agreed upon in the protocol. In case of premature termination or suspension of the study, the Sponsor's study manager will promptly inform the Investigator/institutions and regulatory authorities of the termination or suspension and the reason for that. It is the responsibility of the Principal Investigator (PI) to notify the Institutional Review Board (IRB) in the case of premature termination/suspension.

3.3.4. Withdrawals

The following medical and other reasons justify a premature termination (by subject of Investigator) of any of the study IPs.

- Adverse Event/Serious Adverse Event
- Death
- Protocol Violation (e.g. non-compliance)
- Investigator Judgment
- Pregnancy
- Lost to Follow-up
- Withdrawal by Subject
- Study Terminated by Sponsor
- Other

If a subject withdraws from the study, all efforts will be made to complete a final evaluation, if possible. Subjects discontinued for having experienced an AE will be followed until the AE is resolved, a reasonable explanation is provided for the event, or the subject is referred to his/her own primary medical doctor (PMD). The specific AE in question will be recorded on the appropriate CRF.

[figure not shown]
3.4. Treatments

3.4.1. Investigational Product and Controls

Investigational Product(s):

CCP-020 Topical Ointment

CCP-020 is a topical ointment, 1% (w/w). All excipients used in the topical formulation meet United States Pharmacopeia (USP)/ National Formulary (NF) criteria and are commonly used in

Vehicle

[REDACTED]

CCP-020 topical ointment and vehicle should be stored at room temperature (15°C/59°F to 30°C/86°F). The PI will be responsible for the suitable storage of the IPs in compliance with the storage instructions and must restrict access to the investigative personnel only.

Lot numbers will be given in the clinical study report.

Manufacturer:

[REDACTED]

TWi Pharmaceuticals will be responsible for the manufacturing and filling into the primary package; aluminum tubes. TWi Pharmaceuticals will be responsible to package and distribute to TKL. CCP will be responsible for final release of the product. TKL will be responsible for labeling the product upon site delivery.

The IPs will be dispensed via Eppendorf® Combitips onto separate occlusive patches at approximately 0.2 mL per patch applied once daily for 21 consecutive days.

Controls

Commercially available SLS, prepared as a 0.2% aqueous solution, using United States Pharmacopeia (USP) purified distilled water (e.g., Distilled Water 100% w/v from AquaPhoenix Scientific) by TKL for topical administration, and applied 21 times over consecutive days under occlusive conditions, will serve as a positive control.

A commercially available solution of 0.9% saline for topical administration (e.g., from Medline Industries Inc. (RDI30296)), applied 21 times over consecutive days under occlusive conditions, will serve as a negative control.

Eppendorf® Combitips will be used to apply 0.2 mL of the SLS and saline solutions to their respective occlusive patches.

3.4.2. Description of Investigational Products

The IPs (CCP-020 [Diacerein 1%] topical ointment and vehicle) will be supplied in [product container] for the clinical study. CCP-020 (Diacerein 1%) topical ointment and vehicle were manufactured and packaged in accordance with good manufacturing practice (GMP).

3.4.3. Description of Patch Conditions

CCP-020 (Diacerein 1%) topical ointment, vehicle, negative control, and positive control will be evaluated under occlusive patch conditions by means of application to a 2 x 2 cm Webril® pad. The patches will be secured with nonporous Blenderm tape and hypoallergenic paper tape as needed.

3.4.4. Packaging/Labeling

The study medication tube label will show at least the following:

- Protocol number
- Storage conditions
- Instructions for use
- Expiration date
- Sponsor information
- Investigational drug warning
- Space to enter lot number.

A full product description can be found in the Investigator's Brochure (IB).¹

All study IPs should be stored at room temperature (15°C/59°F to 30°C/86°F).

3.4.5. Assignment to Treatment

3.4.5.1. Randomization

Each subject who signs an informed consent form (ICF) will be assigned a screening number. If the subject meets all of the inclusion and none of the exclusion criteria, and successfully completes the screening procedures, they will be enrolled in the study. Upon enrollment, each subject will be assigned a unique subject number and receive a randomization code, indicating application placement of the study materials. Each subject in this study will serve as his or her own control. All subjects will receive the IPs and control products at adjacent application sites.

The IPs (CCP-020 [Diacerein 1%] topical ointment and vehicle) and study controls (SLS and saline) will be assigned in a randomized sequence to test Sites 1 through 4 using a set of independent 4-by-4 Latin squares. The same study material will be applied to the same test site throughout the study.

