3.5. Visit Schedule and Assessments

3.5.1. Study Procedures and Visit Schedule

Screening

At Screening, the subjects will receive any necessary written and verbal information, and the informed consent of each subject will be obtained. Demographic data (including Fitzpatrick skin type) will be recorded, a medical history will be taken, and previous and concomitant medications will be reviewed. Eligibility will be determined by review of the inclusion/exclusion criteria.

- Any written and verbal information
- Informed consent
- Demographics
- Previous/concomitant medication
- Review of inclusion and exclusion criteria
- Medical history (including lifestyle and habits)
- Examination of application site area

Table 1: Fitzpatrick Skin Types

I	Always burns easily, never tans
II	Always burns easily, tans minimally
III	Burns moderately, tans gradually
IV	Burns minimally, always tans well
V	Rarely burns, tans very well
VI	Never burn, deeply pigmented ^{4,5}

Day 1

Prior to randomization, women of childbearing potential will be administered a UPT. If the subject fulfills all of the inclusion and none of the exclusion criteria, he/she will be allowed participation in the study. A Baseline evaluation of the patch sites will be performed prior to application of the patches to ensure that no conditions, markings, or coloration of the skin will interfere with interpretation of the study results. Subjects will receive a unique randomization number, which determines the application scheme of the study materials for that individual subject.

A set of 4 application sites will be prepared in accordance with the randomization scheme on either the left or right side of the infrascapular area of the subject's back. The choice of left or right side will be made by the investigative personnel based on a visual inspection of skin clarity and will be recorded on the CRF to ensure consistent placement of the patches at subsequent visits. The distance between the patches will be approximately 1 cm. The numbering of the test sites will remain the same throughout the study. A surgical marker will be used to draw lines to indicate the 4 site locations for compliance purposes. All patches will be affixed to the test sites on the intact skin of the infrascapular area of the subject's back by the investigative personnel.

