CCP-020 (Diacerein 1%) topical ointment and vehicle will be applied in the amount of 0.2 mL to a 2 cm x 2 cm Webril® patch pad via Eppendorf® Combitips and then applied to the subject's skin surface as soon as possible following product application. The sterile 0.9% saline (negative control) and 0.2% SLS (positive control) will be applied to a 2 cm x 2 cm Webril® patch pad via pipette and then applied to the subject's skin surface. All 4 products will be evaluated under occlusive patch conditions by means of application to a 2 cm x 2 cm Webril® pad. The patches will be secured with hypoallergenic tape as needed.

Days 2-21

The patches will be removed 24 ± 4 hours after application. Excess study material will be removed with a tissue to avoid the transference of materials between sites by investigative personnel. Investigative personnel responsible for patch application/removal will wipe each site with distilled water. A trained and blinded evaluator will perform an assessment of all test sites for irritation symptoms immediately (within 30 minutes) following patch removal using the scoring system detailed in [Section 3.5.5](#). Scores will be entered into the data sheets by the evaluator. If the skin is not disrupted (skin irritation score ≤ 2), identical treatments and patches will be re-applied to the same test sites with investigational products and control solutions using the procedures above. Separate individuals will be responsible for evaluation of the test sites (blinded) and patch application/removal (unblinded). Individual patches may be discontinued if a reaction of a grade of 3 or greater (see [Section 3.5.5](#)) occurs at any point during the study. Further patch applications of that product on that individual subject will be terminated. A NP symbol and a score of 3 will be assigned for all subsequent days.

The procedure for removal of study materials, evaluation of test sites, and application of fresh study materials will be repeated for 20 consecutive days, for a total of 21 applications per product per subject. A total of 21 post-baseline evaluation scores will be assigned to assess cumulative irritancy.

A new tube of CCP-020 [Diacerein 1%] topical ointment and vehicle will be opened every 14 days due to qualified suitability (see [Section 3.4.2](#)).

In addition, at each of the study visits, concomitant medications and AEs will be reviewed and recorded.

Day 22 (End of Study)

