3.5.5. Safety Assessments

3.5.5.1. Local Tolerability Assessments

Assessment of the patch sites will be conducted by a trained evaluator once at Baseline (Day 1) and then 21 times post baseline during the study ([Table 3](#)). There will be a main evaluator for the study; a backup evaluator will also be assigned in the event that an emergency occurs and the main evaluator is unable to attend the study visit. The following symbols and their respective numerical equivalent Grades will be used to express the response observed at the time of examination ([Table 4](#)).

Table 3: Response Symbols and Numerical Equivalents

Grade	Score*	Definition
0	0	No evidence of irritation
1	1	Minimal erythema; barely perceptible
2	2	Definite erythema, readily visible; or minimal edema; or minimal papular response
3	3	Erythema and papules
4	3	Definite edema
5	3	Erythema, edema, and papules
6	3	Vesicular eruption
7	3	Strong reaction spreading beyond test site

*Scores are utilized only during the statistical analysis process of the study. Grades will be conducted throughout the study by the trained evaluator.

Table 4: Effects on Superficial Layers of Skin

Grade	Score*	Response
A	0	Slight glazed appearance
C	1	Marked glazing
E	2	Glazing with peeling and cracking
F	3	Glazing with fissures
G	3	Film of dried serous exudate covering all or portion of the patch site
H	3	Small petechial erosions and/or scabs

*Scores are utilized only during the statistical analysis process of the study. Grades will be conducted throughout the study by the trained evaluator.

Other notations (see [Table 5](#)) may be made in place of a score to designate particular circumstances preventing the assignment of a score or in addition to a score to identify damage to the epidermis and/or spreading of a reaction beyond the patch site.

The actual patch test grades are a combination of a numerical ([Table 3](#)) and letter ([Table 4](#)) grades consistent with the definitions given in the grading scales. However, in order to determine discontinuation of a patch site (grade > 3) and to perform statistical analyses, grades containing letter grades have to be converted to numerical equivalents. These are converted as follows: A=0, C=1, E=2 and F, G, and H=3. These equivalents are considered additive to any numerical score (e.g., 2C=2+1=3), in this case the patch site would be discontinued.

Table 5: Other Notations

Notation	Definition
X	Subject absent
B	Burning or stinging sensation
PD	Patch dislodged

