NA	Patch not applied
NP	No patch due to limiting irritation
I	Itching
D	Damage of the epidermis: oozing, crusting, and/or superficial erosions
p	Papular response
pv	Papulovesicular response
S	Spreading of reaction beyond patch site (i.e., reaction where study material did not come in contact with skin)
T	Tape related reaction

Details regarding the statistical analysis of the cumulative irritation scores are provided in [Section 4.0](#).

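### The Latin squares balance site position but not neighbours, so products may sit unequally often beside SLS; neighbour-balanced squares would limit this at no cost if the sites form a row

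*Combined protocol and SAP*

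**What the plan says.** Section 3.4.5.1 says that the two investigational products and the two controls are randomised to Sites 1 to 4 "using a set of independent 4-by-4 Latin squares". It adds: "The same study material will be applied to the same test site throughout the study". It describes the sites as adjacent: "All subjects will receive the IPs and control products at adjacent application sites". Section 3.5.1 (Day 1) gives the spacing: "The distance between the patches will be approximately 1 cm". No section says whether the four sites form a single row or a 2 x 2 block, or how the squares are chosen.

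Three places anticipate that material or a reaction may leave its site. Grade 7 in Table 3 (section 3.5.5.1) is "Strong reaction spreading beyond test site". Notation S in Table 5 is for a reaction on skin that the material did not touch. In section 3.5.1 (Days 2-21), excess material is removed with a tissue "to avoid the transference of materials between sites by investigative personnel", and each site is then wiped with distilled water.

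Section 4.6.1 analyses the mean cumulative irritation score with an ANOVA on subject and product only.

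**The concern.** A Latin square puts each product once at each site position, but says nothing about which products are next to each other. SLS is the known irritant. If its reaction or material reaches a neighbouring site, that neighbour's score rises. Because sites are fixed, a product placed beside SLS stays there for all 21 applications.

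If CCP-020 lies beside SLS in more subjects than vehicle or saline does, CCP-020 looks more irritating than it is; if in fewer, less irritating. The planned model has no term for this. A site-position term would not remove it either, because position is already balanced.

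**Working it through.** **Inputs.** From the protocol: 4 x 4 squares, fixed sites, 30 evaluable subjects (7 complete squares and 2 rows of an eighth), and scores from 0 to 3 per reading. Assumed, because the documents do not say: four sites in a row; squares drawn freely from all possible 4 x 4 squares; spill of 0.2 to 0.6 mean-score units at a site beside SLS. The plan states no adjacency figure to reproduce.

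**Step 1: one square.** There are 576 Latin squares of order 4. For each, count the rows (subjects) in which CCP-020, vehicle and saline lie beside SLS.
- 144 squares give (2, 2, 2). All 144 are also balanced for every other pair of products.
- The other 432 (432/576 = 75%) are unequal, for example (4, 1, 1), (0, 3, 3) or (4, 0, 2).
- Over all 576 squares, each product averages 2 rows in 4.

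Let D be the number of subjects with CCP-020 beside SLS minus the number with vehicle beside SLS. Within one square:

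| D | Squares |
|---|---|
| 0 | 240 |
| +2 or -2 | 96 |
| +3 or -3 | 192 |
| +4 or -4 | 48 |

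The mean is 0 and the variance is (96 x 4 + 192 x 9 + 48 x 16)/576 = 2880/576 = 5.

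**Step 2: comparison with unrestricted randomisation.** If each subject's order were drawn independently, the variance of D would be 2/3 per subject, or 4 x 2/3 = 2.67 per four subjects. The square gives 5 because its rows tend to share adjacencies. Free Latin squares therefore do not average adjacency out; they make its imbalance larger.

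**Step 3: 30 subjects.**
- Seven squares contribute 7 x 5 = 35. The covariance between two rows of a square is (5 - 8/3)/12 = 7/36, so the last two rows contribute 2 x 2/3 + 2 x 7/36 = 1.72. The total is 36.72, and the SD of D is √36.72 = 6.06.
- The 95% range is -12 to +12 and the median of |D| is 4. |D| is 8 or more in 22% of lists and exactly 0 in 6%.
- Unrestricted randomisation gives SD √(30 x 2/3) = √20 = 4.47.
- With neighbour-balanced squares, D is 0 in every complete square. The two extra rows leave D = 0 in 112 of 144 cases and ±2 in the other 32.

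**Step 4: shift in the contrast.** Shift = spill x D/30.

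| Absolute D | Spill 0.2 | Spill 0.6 |
|---|---|---|
| 4 (median) | 0.03 | 0.08 |
| 8 | 0.05 | 0.16 |
| 12 (limit of 95% range) | 0.08 | 0.24 |

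**Step 5: error rate.** A simulation of CCP-020 versus vehicle used a paired t test at 32 subjects, assumed spill of 0.1 to 0.5 and assumed paired SD of 0.3 to 0.8. The false-positive rate was 4.9% to 12.1% with free squares and 0.2% to 5.1% with balanced squares. The highest rate came from spill 0.5 with SD 0.3; with spill 0.1 and SD 0.8 the two designs hardly differed (4.9% and 5.1%).

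**Step 6: 2 x 2 block.** If sites sharing an edge count as neighbours, SLS has two neighbours in each subject, so 8 adjacencies per square over three products. Since 8/3 is not a whole number, none of the 576 squares can balance them. Three squares can: (4, 2, 2), (2, 4, 2) and (2, 2, 4) sum to 8 each.

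**The case against.** The tempting stronger reading is that the design biases the CCP-020 contrasts. The documents do not support it for vehicle or saline: every product has the same expected number of SLS neighbours, so the mean shift over the randomisation is zero and its sign cannot be predicted. What remains is added variance and a shift tied to the list actually drawn.

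It would also go too far to say that the protocol specifies unconstrained squares. It does not exclude balanced ones; it only fails to require them. The figures above depend on a free draw and on a row, and neither is stated.

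Evidence that spill matters is limited. Grade 7 scores the site that is reacting, not its neighbour. Notation S lets spread be flagged. Sites are wiped daily, and sections 3.3.3 and 3.5.1 allow a patch to be discontinued at grade 3 or greater, which may end SLS exposure at a strongly reacting site. No spill size, SD or decision threshold is given. All of this stands, and the effect may be negligible. But wiping happens only at patch removal and cannot stop migration during about 24 hours of occlusion or spread through the skin, and flagging S does not correct a neighbour's score.

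Finally, an SLS-neighbour covariate could be added in the SAP, which section 4.1 says is still to be finalised. That is a fair complement, since the allocation list is known, but it does not make balance at the design stage less worthwhile.

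**Conclusion.** The point holds as a free improvement, not as a flaw that invalidates the analysis. Under a row layout and a free draw, one list for 30 subjects will typically leave CCP-020 and vehicle differing by about 4 subjects in SLS adjacency, and by 8 or more in about one list in five. The same holds for CCP-020 versus saline by symmetry. The resulting shift is small on a 0 to 3 scale unless spill is substantial.

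A reader might infer that balancing cures every contrast. It does not. Under either design, in a row, about half of the CCP-020 sites lie beside SLS, so CCP-020 versus SLS shrinks by about 0.5 x spill (0.1 to 0.3 for the assumed range).

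Confidence is firm on the counting and moderate on its importance, because layout, draw and spill are all assumptions.

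**What to change.** In section 3.4.5.1:
- State the site layout and the rule for selecting squares.
- For a row, draw only from the 144 neighbour-balanced (Williams-type) squares, with rows and product labels randomised. Each pair of products is then adjacent in exactly 2 of every 4 subjects. D is 0 per complete square and at most 2 at 30 subjects; randomising 32 would complete the last square.
- For a 2 x 2 block, balance SLS neighbours over sets of squares (three at a time suffice), since no single square can do so.

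Dropouts weaken the limit. If, say, 36 were randomised and 6 lost at random, |D| would exceed 2 in about 17% of lists, against about 67% with free squares.

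Also reconcile the fixed-site rule in section 3.4.5.1 with section 3.3.3, which provides for a change of site location after a reaction. Moving a patch alters adjacency.

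For a row, the cost is a change to the randomisation program only: no extra subjects (unless 32 are chosen), visits or materials.
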